these patients will suffer a critical respiratory event (CRE), defined as significant oxygen desaturation, respiratory failure, need for airway support and manipulation, aspiration of gastric contents or need for tracheal re-intubation.¹¹ Obviously, elderly patients or those with pre-existing pulmonary disease, obese patients, patients with hypothermia, hypoventilation, hypercarbia, those receiving antibiotics that potentiate NMBA block, etc. are at increased risk of CREs. Sugammadex has been shown to effectively and completely reverse NMBAs, and its use avoids residual neuromuscular block.¹²

D. Rationale for Proposed Research:

Assessment and management of respiratory function following NMB has been complicated by the lack of a cohesive and continuous monitoring system to guide clinical decisions. In conjunction with quantitative TOF measurements, continuous, quantitative respiratory monitoring using the ExSpiron System will be particularly useful in detecting residual NMB leading to varying degrees of respiratory depression. Recent data have shown that stratification of patients based on the ExSpiron MV as % of predicted MV (MV_{PRED}), prior to opioid dosing has made it possible to identify patients who are at risk for further decreases in MV and opioid-induced respiratory depression. In the proposed trial, we use the ExSpiron to assess the respiratory effects of residual NMB and the effects of sugammadex reversal in decreasing the incidence of pulmonary complications (CREs).

2.3 Study Design	Research Plan A. Experimental Design: Randomized Controlled Blinded Trial B. Sample size and statistical analysis: (See Section 2.7 below) C. Subject Criteria: 1) Inclusion Criteria: Patients undergoing surgery with general anesthesia Patients scheduled to receive rocuronium or vecuronium for neuromuscular blockade Patients weighing \geq 80 pounds Non-intubated patients prior to surgery Patients who are able to give informed consent. 2) Exclusion criteria: Patients unable to give informed consent. Patients scheduled to receive nonsteroidal neuromuscular blocking agents (succinylcholine or benzylisoquinolinium) Patients scheduled to receive steroid neuromuscular blocking agents other than rocuronium or vecuronium. Any patient whose condition will not allow for placement of the electrode PadSet. Patients whose tracheas were not extubated in OR or PACU. Pregnant women. Patients with known severe renal impairment (estimated creatinine clearance $<$ 30 mL/min) as documented in the medical record. Patients with known hypersensitivity to sugammadex or any of its components. 3) Withdrawal/Termination Criteria: Participants may withdraw from the study at any time for any reason, Investigators may terminate the study if this is determined to be in the best interest of the subject.
------------------	---

D. Risk/Benefit Assessment:

Sugammadex. Sugammadex has been FDA approved for clinical use in the US and it has been used worldwide since 2008. We plan to administer the smallest dose of sugammadex recommended for shallow neuromuscular block (2 mg/kg of actual body weight), a dose that has not been reported to cause allergic or any other side effects. The use of sugammadex may lead to complete reversal of residual neuromuscular block, and avoidance of the respiratory complications (CREs) associated with incomplete reversal after neostigmine.

TOF Measurement. This involves delivery of small electrical impulses from a nerve stimulator via surface ECG electrodes to a peripheral nerve (usually the ulnar nerve at the wrist) and measuring the muscle contraction in the innervated muscle (usually the adductor pollicis muscle or the thumb. This testing is used routinely in many centers in awakening patients in the PACU, and it is not associated with any adverse effects or patient discomfort. In fact, routine monitoring has been advocated routinely for decades, as it both decreases the incidence of CREs and other postoperative complications and increases patient satisfaction.^{11,12}

[figure not shown]
ExSpiron Respiratory Volume Monitoring (RVM). The RVM device has been FDA cleared and is currently in clinical use. It is considered a “non-significant risk device”. The device requires the application of monitoring PadSets to the patient’s skin similar to EKG electrodes and, as such, poses minimal risk. It is possible that the electrodes may irritate the skin. The presence of skin irritation will be monitored and treated appropriately, and further subject participation will cease if it is significant. Collected data up to that point will be used for the study, unless the subject requests otherwise. Direct physical harm is extremely unlikely. Any adverse events will be documented and forwarded to the IRB as per adverse event (AE) reporting requirements.

There is always a risk for breach of confidentiality despite best efforts.

Categories of Risk:

- 1) Physical Risk: Sugammadex administration may result in temporary changes in taste sensation (dysgeusia); allergic reactions have been reported exceedingly rarely at the dose we plan to administer (2 mg/kg). Rare allergic reactions have been reported in patients receiving the highest dose indicated, 16 mg/kg, which is 8times higher than the dose we plan to

	
administer.
 
Cases of marked bradycardia, some of which have resulted in cardiac arrest, have been observed within minutes after administration. Clinicians and study team members will be instructed to monitor for hemodynamic changes and administer anticholinergic agents such as atropine if clinically significant bradycardia is observed.
 
Patients with pulmonary history should be monitored for a potential risk of developing bronchospasm immediately or a few minutes after administration of sugammadex.
 
Women who are sexually active and use hormonal contraceptives, will be instructed to use an additional non-hormonal method of contraception (Barrier methods (such as a condom or diaphragm) used with a spermicide (a foam, cream, or gel that kills sperm); Intrauterine device (IUD); Abstinence (no sex)) for 7 days following study drug administration.
 
TOF Monitoring – this type of monitoring is recommended in all patients receiving neuromuscular blocking agents, and is used routinely intraoperatively and postoperatively in the PACU (and in the ICU) to detect residual neuromuscular block. This type of monitoring has been shown to reduce the incidence of CREs.
 
The ExSpiron is a non-invasive and safe device cleared by the FDA for monitoring MV, TV and RR. Prior to study start, the device and its components will undergo a standard safety check by the institutional medical engineering department. There is a minimal risk of skin irritation from the electrode PadSets, the same as for EKG pads.
 
2) Psychological Risk: There is no known psychological risk to the participant. The study will be explained to them and they will be given the opportunity to ask questions. They will be informed that they can withdraw from the study at any time for any reason.
 
3) Social Risk: There is no known social risk to the patient. Participation in the study will not affect the subjects' ability to interact with family and friends post-operatively.
 
4) Economic Risk: There is no cost to the patient and their standard care will be unaffected.
 
Benefit to Participating in the Study: There are no direct benefits to subjects from participating in this research; however, information obtained from this study may benefit future patients.

--	---

A. Specific Methods and Techniques used Throughout the Study:

300 patients undergoing surgical procedures requiring general anesthesia with mechanical ventilation will be recruited and consent will be obtained. The subjects will be randomized preoperatively to receive in the OR following the procedure and prior to extubation either sugammadex (Group 1, n=150 patients) or placebo (Group 2, n=150 patients). In all patients, intraoperative surgical and anesthetic management will follow the usual clinical routine at the two enrolling institutions. Once surgery is finished, emergence from anesthesia will occur as per usual clinical routine until the clinician determines that the patient is ready for tracheal extubation. Once the decision to extubate the trachea is made, the patient will receive intravenously either sugammadex 2 mg/kg or placebo in a blinded manner. The patient's trachea will be then extubated, and postoperative anesthetic care will proceed as per usual routine. Patients will then be transferred to the PACU for postoperative care and recovery. (This methodology will ensure that all 300 patients will receive at least the current standard of clinical care. Of the 300 patients, 50% of them (n=150 patients) may benefit from the administration of sugammadex,

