Randomized Double---Blinded, Controlled
Trial to Compare the Effectiveness of
Sugammadex vs. Placebo to Prevent
Residual Neuromuscular Block in the Post---
Anesthesia Care Unit as Evaluated with a
Non---Invasive Respiratory Volume Monitor

NCT02728726

6/29/2017

f

Merck Investigator Studies Program (MISP) Protocol Template

Requirements for Submitting a Full Proposal

Section #1 - MISP Protocol Identification

Study Title:	Randomized Double-Blinded, Controlled Trial to Compare the Effectiveness of Sugammadex vs. Placebo to Prevent Residual Neuromuscular Block in the Post-Anesthesia Care Unit as Evaluated with a Non-Invasive Respiratory Volume Monitor
Request Date:	Protocol Version date 6/29/17
Institution Name:	Mayo Clinic, Jacksonville University of Texas - UT Health, Houston
Investigator Contact Information:	J. [name] Assistant Professor of Anesthesiology Department of Anesthesiology Mayo Clinic [name] O: [contact] E: [contact] [name] The University of Texas, UTHealth Department of Anesthesiology [name] [REDACTED] [REDACTED]

Section #2- Core Protocol

The Primary objective of this study is to determine whether patients who receive sugammadex immediately after tracheal extubation will exhibit a decrease in the incidence of postoperative residual paralysis and an associated decrease in the incidence of postoperative respiratory depression (which can precede critical respiratory events, CRE).

The Secondary objectives are to: a) determine whether patients receiving sugammadex will have a normal TOF ratio (>0.90) indicative of full neuromuscular recovery in the PACU; and b) to improve patient safety by documenting whether postoperative respiratory depression (decreased MV below 80% and 40% of predicted MV as assessed by a Respiratory Volume Monitor) is due to opioid administration vs. postoperative residual neuromuscular block (by comparing postoperative VAS scores and total opioid administered).

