general anesthesia and planned extubation in the OR. After a thorough review of the study. Sufficient time will be given to the patients, parents, guardians or legal representative to ask questions and decide on participation.

- d. Location where study will be performed: University

	
of Texas, UTHealth at Houston and Mayo Clinic, Jacksonville, Florida operating holding areas, operating and recovery rooms, and intensive care units as applicable.
 
e. Personnel who will conduct the study include PI and research team members.
 
10) Subject fees: There are no fees for this study.
 
11) Procedures to protect subject confidentiality: A unique study ID number will be assigned to each subject as a means to de-identify the study data. A code will be kept separately with the PI. Study files will be kept in a locked office in a locked cabinet or a password-protected computer with encrypted study files. The location will be the PI office with restricted access. The code will be locked separately from study files in the PI office.
 
a. Certificate of Confidentiality: N/Ab. How data will be coded, recorded, and stored to protect confidentiality: All data will be de-identified. All data will be linked to the subject study ID by a code.c. Data will be analyzed by institutional biostatisticians at UTHealth at Houston.d. Parties who will have access to the data, including the key to the identity code: only [name] and J. [name] and primary study staff will have access to the master study log/key. Other investigators and the clinical and engineering staff at Respiratory Motion, Inc. will only have access to de-identified data.e. Parties who will have access to research records: Investigators on the study, Respiratory Motion, Inc. will have access only to de-identified records.f. Collaboration: This study is performed in collaboration with Respiratory Motion, Inc.g. Alternatives: The alternative to participating in this study is not participating.h. How new information will be conveyed to the study subject and how it will be documented: Other than the initial explanation of the purpose and plan for the study, we don't expect new information to
--	---

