	
become available from the study that could affect a subject's willingness to participate. No new information of clinical relevance to the subject is expected from this study. Therefore no new information will be given to the patient.
 
 i. Payment: The participants will not be compensated for their participation in the study. j. Payment for a research-related injury: This is a minimal risk study. There are no plans to provide other compensation. If a participant is injured during this study, the study doctor will discuss the available medical treatment options with the subject. 
12) Outcome: The primary outcome of this study is evaluation of the effects of sugammadex on the incidence of respiration complications postoperatively.

2.6 Study Duration	We anticipate that we will recruit the planned number of patients (n=300) at the two centers (UTHealth and Mayo Clinic) within 6 months of IRB approval and receipt of all necessary study materials and medications.

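### Exclusion for not being extubated is settled only after randomization, and possibly after dosing, so it can remove randomized patients on an outcome linked to the endpoints

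*Combined protocol and SAP*

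**What the plan says.** **Exclusion.** Section 2.3 C.2 excludes "Patients whose tracheas were not extubated in OR or PACU". This describes something that has happened. The criteria on blocking agents beside it are worded by what is scheduled.

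**Randomization and dosing in the procedures.** Section 2.5 A: "The subjects will be randomized preoperatively to receive in the OR following the procedure and prior to extubation either sugammadex" or placebo. Then: "Once the decision to extubate the trachea is made, the patient will receive intravenously either sugammadex 2 mg/kg or placebo in a blinded manner". After that the patient's "trachea will be then extubated, and postoperative anesthetic care will proceed as per usual routine". Section 2.5 B.2 also puts administration before extubation.

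**Dosing in the objectives.** The primary objective in Section 2 concerns "patients who receive sugammadex immediately after tracheal extubation", and hypothesis A in 2.1 likewise puts the drug after extubation. Section 2.5 B.3.ii mentions extubation and then the dose, without fixing the order.

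**Consent population.** Section 2.5 B.9.c seeks consent from patients with "general anesthesia and planned extubation in the OR". That can be known beforehand, but it names the OR only, whereas 2.3 says OR or PACU.

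**Outcome and analysis.** Section 2.5 B.12 gives the primary outcome as the "effects of sugammadex on the incidence of respiration complications postoperatively". Section 2.7 B.a.vii compares respiratory complications, respiratory interventions and transfer to ICU or step-down. Section 2.7 C makes A1 the primary hypothesis and A2 the key secondary. Section 2.7 defines no analysis set and gives no rule for a randomized patient who is not extubated. Section 2.9 ends the study once data are accrued in 300 patients, 150 per arm, which can be read as replacing excluded patients.

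**The concern.** An exclusion protects a randomized comparison only if it is settled before randomization or cannot be influenced by the assigned treatment. Extubation status fails the first condition under either dosing order. Under the order in 2.5 A it can also fail the second. Residual block can prevent extubation, the study drug can change residual block, and an adverse reaction between injection and extubation could also leave a patient intubated.

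A dosed patient who cannot be extubated is an obvious candidate for a respiratory complication, an intervention or an ICU transfer. Dropping such patients removes those events from the arm in which they occurred. Losses from placebo would understate a benefit. Losses from sugammadex would overstate it and hide a safety event.

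**Working it through.** **1. Timing under each dosing order**

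| Order | Exclusion relative to randomization | Exclusion relative to dose |
|---|---|---|
| Drug before extubation (2.5 A, 2.5 B.2) | After | Before, if no decision to extubate is made; after, if a dosed patient is then not extubated |
| Drug after extubation (Section 2 objective, hypothesis A) | After | Before: a patient never extubated is never dosed |

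Only the dosed-then-not-extubated case lets the drug affect who is excluded. In the other cases the patient has received nothing and the decision is made blind, so treatment cannot drive the exclusion.

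**2. The plan's own figures**

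Section 2.7 D uses n = 2·p̄(1−p̄)(Zβ+Zα)²/Δp².

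- A1, 33% vs 15%: 2 × 0.24 × 0.76 × (0.84+1.96)² / 0.18² = 88.27, against 88.3 stated.
- A2, 22% vs 11%, one-sided: 2 × 0.165 × 0.835 × (0.84+1.645)² / 0.11² = 140.6, against 143.2 stated, a difference of 1.8%.

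The planned 150 per arm covers both. The issue is bias, not sample size. If patients are lost for reasons unrelated to outcome, 5% per arm (142 left) lowers normal-approximation power from 95.8% to 94.8% for A1 and from 82.4% to 80.6% for A2 (one-sided).

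**3. How many patients?**

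The documents give no non-extubation rate. The nearest figure is in 2.2 C: critical respiratory events in 0.8% of patients.

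- If the base is everyone given a blocking agent: 0.008 × 150 = 1.2 per arm.
- If the base is only those with residual block, up to 40%: 0.008 × 0.40 × 150 = 0.48 per arm.

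That definition lists re-intubation and does not name failure to extubate, so it is only a yardstick. It points to about one patient per arm or fewer. The range of 2 to 6 below is an assumption on the high side.

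**4. Effect on the A1 placebo rate**

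Take 50 events in 150 and remove k patients who would all have been events: (50−k)/(150−k).

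| k | Rate |
|---|---|
| 0 | 33.3% |
| 1 | 49/149 = 32.9% |
| 2 | 48/148 = 32.4% |
| 4 | 46/146 = 31.5% |
| 6 | 44/144 = 30.6% |

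The planned 18-point difference moves by about 0.4 points at k = 1 and by 0.9 to 2.8 points at k = 2 to 6.

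**5. Effect on the tests**

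This is an exact enumeration of the Fisher test, taken as two-sided at 0.05, with 150 per arm before exclusion and k events removed from one arm only.

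| k | A1 power (33% vs 15%), lost from placebo | A2 power (22% vs 11%), lost from placebo | A1 rejection, no true effect (33% both) | A2 rejection, no true effect (22% both) |
|---|---|---|---|---|
| 0 | 94.8% | 68.2% | 3.7% | 3.6% |
| 2 | 93.3% | 63.5% | 4.9% | 5.0% |
| 6 | 87.0% | 42.7% | 8.0% | 9.9% |

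The k = 0 power for A2 is below 80% because the plan sized A2 one-sided. That is a separate matter.

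**6. Rare outcomes**

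The documents give no ICU-transfer rate. If a complication is expected in about one patient per arm (step 3), removing a single event can remove every event in that arm.

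**The case against.** The strongest case on the other side is that almost nobody will be affected. The drug is given only after standard reversal, after the clinician judges recovery adequate, and after the decision to extubate. Patients extubated late in the PACU, or extubated and then re-intubated, are not excluded. Under the objective's order no dosed patient could meet the criterion at all. No sentence in 2.7 drops these patients from the analysis; the criterion could be read in the light of the consent section as planned extubation; and 2.5 B.8 follows all patients for drug complications. All of this stands, and it limits the size.

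It does not remove the point. The criterion is worded as an event, the procedures place the dose before that event, and 2.7 does not say who is analysed. Following all patients for complications does not settle whether they count in the Fisher comparisons.

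A reader might infer that the trial will lose its worst respiratory failures, mostly from placebo, and that the primary result is materially biased. The documents do not support that. They give no rate, the 0.8% figure suggests few cases, re-intubated patients stay in, and non-extubation may have causes unrelated to block. The direction is not fixed.

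A reader might also want non-extubation scored as an A1 and A2 event in the main analysis. Such a patient may have neither minute-ventilation window, and scoring unrelated non-extubation as respiratory depression would change both endpoints. It belongs in a sensitivity analysis.

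**Conclusion.** The point holds in limited form. The exclusion always falls after randomization. Under the order in 2.5 A it can also fall after dosing, where the drug may influence it. With no analysis set in 2.7, following the text can remove randomized and dosed patients on an event related to the respiratory and ICU-transfer endpoints, with bias possible in either direction.

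The likely effect on A1 is small: about 0.4 points on the placebo rate for one lost event, and up to about 2.8 points for an assumed six. The larger power and error-rate shifts for A2 require several losses, all from one arm and all events, which the documents do not make likely. The practical risk lies in comparisons of rare complications and ICU transfer, where one missing event counts. All sizes rest on assumed numbers of non-extubated patients.

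**What to change.** - In 2.3, restate the criterion as planned extubation, known before randomization. Reconcile its OR or PACU wording with the consent section, which names the OR only.
- Reconcile the dose-before-extubation and dose-after-extubation statements in Section 2, 2.1 and 2.5.
- In 2.7, state that every randomized patient who received study drug is analysed in the assigned group.
- Keep dosed but non-extubated patients in the adverse event, respiratory intervention and ICU-transfer comparisons of 2.7 B.a.vii.
- Report all non-extubated patients by arm, dosed and undosed separately, and state whether anyone is replaced under the accrual rule in 2.9.
- For A1 and A2, where these patients may have no minute-ventilation window, run sensitivity analyses with them scored as events and with them left out.

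The cost is one reworded criterion and a few sentences in 2.7. The downside is that a few patients will lack respiratory volume data and be handled by rule.

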	
available for patient care decisions, but the continuous respiratory trace will be displayed. Patient care providers should not use this trace for clinical decision-making. If the trace is absent or grossly abnormal, this should be recorded and study staff notified to ensure proper device function.
 
f. TOF data will be hidden and not available for patient care decisions
 
6) Final Discharge Parameters: Record the patients' final discharge date and time (LOS) from the PACU.
 
7) De-identification: All study data will be de-identified and identifying information will be linked to a code only accessible to the study staff. The code will be destroyed following final data analysis.
 
8) Assessment of Subject Safety and Data Safety Monitoring Plan: All patients will be followed by one of the study investigators to ensure there are no complications associated with sugammadex administration (flushing, tachycardia, hypotension, etc). There are no expected complications of RVM monitoring. There are no expected complications associated with TOF monitoring, and in fact, such monitoring has been shown to improve patient safety by decreasing postoperative CREs and other complications.^{11,12} External monitoring will not be provided; however, Principal Investigator will review all data for accuracy to ensure adherence to the approved protocol. Data will be recorded by the study coordinator and all electronic study-related files will be stored on a secured Mayo Clinic server. Drug accountability and dispensing will be handled by pharmacy. Any potential adverse events will be assessed by the principal investigator for severity and relevance to the study drug.
 
9) Subject Participation:
 
 Recruitment: Subjects will be recruited in the pre-procedure holding areas by the study team members prior to their surgery. Screening Interview: Subject screening will be based on study personnel examining the surgery schedule of the next or same day to identify appropriate procedures scheduled and patient's eligibility. Informed consent process and timing of obtaining of consent: Informed consent will be obtained by the study staff prior to surgery in the preoperative holding area, in patients requiring surgery and
--	---

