2.9 Adverse Experience Reporting

1) Definition of Serious Adverse Event (SAE) and Adverse Event (AE): The PI and co-investigators will ensure that all patients have appropriate study consent and that protocols are followed. Data collection and device use pose minimal risk that cannot be further categorized.

- a. Reporting timeframe for serious adverse events (SAEs) and adverse events (AEs): Any adverse event will be reported by study personnel to the IRB per IRB standard protocol. Any SAE will be reported by the PI to the IRB within 24 hours along with a detailed report and enrollment will cease until the IRB has reviewed the event.
- b. Accountability procedures as they relate to drugs, devices, and data: Data to be collected will include device measurements of patient respiratory impedance values, during the procedure and after the procedure. Data regarding patient demographics, height, weight, any relevant pulmonary medical or surgical history and any complications will be obtained from the medical record. Data collected from each subject by the ExSpiron device will be stored under the subject's study ID. All other data collected will be stored electronically under the subjects study ID. Data collection sheets will be used to collect information regarding vital signs, medications and events. All information will be de-identified and protected in a secure office by either lock or key or password protection on a secure computer in the PI office. The code will be a paper folder kept under lock and key in a cabinet separate location from other study data files in the PI office. PI and co-investigators will be responsible for monitoring study data collection. The study will be stopped when we reach the endpoint of accruing data in 300 patients (150 in each arm) or if the Data Safety Monitor deems it necessary.

2.10 Itemized Study Budget	Please see attached budget worksheet.

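### Significant skin irritation from the RVM PadSet ends the patient's whole participation, although only the RVM recording depends on the pad

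*Combined protocol and SAP*

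**What the plan says.** The rule is in section 2.3 D, in the paragraph on ExSpiron Respiratory Volume Monitoring. Irritation is to be watched for and treated, and then: "further subject participation will cease if it is significant. Collected data up to that point will be used for the study". The data are left out only if the patient asks for that. The plan does not define what counts as significant. Later in the same section, under physical risk, it says: "There is a minimal risk of skin irritation from the electrode PadSets, the same as for EKG pads". No rate is given.

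Three other places bear on the rule:

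- Section 2.3 C.3 (Withdrawal/Termination Criteria) is general: "Participants may withdraw from the study at any time for any reason". It does not distinguish giving up a device from giving up follow-up.
- Section 2.5 B.8 (safety monitoring) makes no exception for irritation: "All patients will be followed by one of the study investigators to ensure there are no complications associated with sugammadex administration".
- Section 2.9 takes complications from a source that needs no monitor: "any relevant pulmonary medical or surgical history and any complications will be obtained from the medical record".

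Section 2.7 names no analysis set and gives no rule for missing data.

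**The concern.** The PadSet is a measuring device. Taking it off ends one data stream, but the rule as worded ends them all. If irritation appears after the study drug has been given, the randomised exposure is already complete, and a local reaction to a chest electrode is no reason to stop recording how the patient fares.

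What is at stake is avoidable missing data after randomisation. The affected outcomes are not peripheral. Residual paralysis, measured by TOF, is part of the primary objective in Section #2, and section 2.5 B.12 calls the effect on respiratory complications the primary outcome, even though section 2.7 C assigns the formal primary test to Hypothesis A1.

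There is also a consistency problem. One site could read 2.3 D as ending all contact with the patient for study purposes, while another could read 2.5 B.8 as requiring follow-up of the same patient.

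**Working it through.** **Step 1. Which outcomes need the PadSet?**

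| Outcome | Source in the plan | Needs PadSet? | Serves |
|---|---|---|---|
| MV in the 15-30 minute window | 2.7 B.a.i, B.b.i | Yes | A1 |
| MV in the last 30 minutes | 2.7 B.a.ii, B.b.ii | Yes | A2 |
| Other MV measures | 2.1, 2.7 | Yes | B, C, D, H, I |
| PACU length of stay | arrival and discharge times, 2.5 B.5-6 | No | E |
| Respiratory complications, interventions, ICU or step-down transfer | 2.7 B.a.vii; 2.9 | No | F |
| TOF ratio | own skin electrodes on the forearm, 2.5 B.3.ii | No | G |
| Medications, opioid total, pain scores | 2.5 A.8-9; 2.7 B.b.iv-v | No | secondary comparisons |

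The last four rows would stop under the literal rule without need. The first three stop whenever the pad comes off, whatever the wording.

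**Step 2. When can the rule apply?** The PadSet goes on before the procedure (2.5 B.3.i), and the study drug is given once the decision to extubate is made (2.5). Irritation could therefore be noticed before or after dosing. The argument about a completed exposure applies to the second case.

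**Step 3. How many patients?** No rate is stated, so it has to be assumed. With 300 patients: 0% gives 0; 1% gives 0.01 × 300 = 3; 5% gives 0.05 × 300 = 15; an extreme 10% gives 30. The relevant rate is that of irritation judged significant and seen early enough to cut off data.

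**Step 4. Does it threaten the sample size?** The plan's formula is n = 2·p̄(1−p̄)(Zβ+Zα)²/Δ².

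- Primary, 0.33 vs 0.15: 2 × 0.24 × 0.76 × (0.84+1.96)²/0.18² = 88.27, against 88.3 stated.
- Key secondary, 0.22 vs 0.11, one-sided: 2 × 0.165 × 0.835 × (0.84+1.645)²/0.11² = 140.6, against 143.2 stated (1.8% apart).

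Both reproduce closely. For power at a reduced n per group, the normal approximation is Φ{[Δ√n − Zα√(2p̄(1−p̄))]/√(p₁q₁+p₂q₂)}, where q = 1−p. For the primary at n = 150 this is Φ{[0.18 × 12.247 − 1.96 × 0.604]/0.590} = Φ(1.73) = 95.8%.

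| Assumed loss | n per group | Primary power | Key secondary power (one-sided, as planned) |
|---|---|---|---|
| 0% | 150 | 95.8% | 82.4% |
| 1% | 148 | 95.6% | 82.0% |
| 5% | 142 | 94.8% | 80.6% |
| 10% | 135 | 93.8% | 78.8% |

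These figures are a ceiling on the effect of losing RVM data, and rewording the rule would not recover that loss. They show that the point does not turn on power. The plan gives no power calculation for Hypotheses E or F, and its general residual-block calculation (2.7 D) is not tied to Hypothesis G. For these, the loss is best stated as the patient counts in Step 3.

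**The case against.** The strongest reply is that this is a rare event with little consequence. The plan likens the risk to that of ordinary EKG pads, and only significant irritation triggers the rule. Both arms wear the same PadSet under double blinding, so nothing in the documents suggests that such exits would differ by arm. Hypotheses E, F and G are formally tested only if A1 and A2 both succeed (2.7 C). All of this stands, and it keeps the point small. It does not explain why the plan should discard outcomes that the pad does not affect.

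A reader might infer more than the text supports, in four ways:

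- **That drug-safety data are lost.** The RVM paragraph itself says adverse events will be documented and sent to the IRB, 2.5 B.8 follows all patients, and 2.9 draws complications from the medical record and requires SAE reports within 24 hours. This is an unreconciled conflict, not a demonstrated loss.
- **That adverse reactions can be deleted from the record.** Use of collected data is the default, and only the patient's own request changes that. Nothing says such a request reaches adverse-event reports.
- **That A2 is always lost.** Irritation found at discharge or at final pad removal leaves the last 30 minutes already recorded.
- **That the patient's right to withhold data should be struck out.** That depends on consent and IRB terms that the documents available for review do not contain.

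TOF also uses skin electrodes. They are separate from the PadSet, but a patient who reacts to one adhesive may react to another, so continued TOF cannot be taken for granted.

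**Conclusion.** The concern holds in a limited form. Section 2.3 D makes significant PadSet irritation the end of the patient's participation when only RVM recording depends on the pad, and it is not reconciled with 2.5 B.8. On a literal reading, later TOF, length of stay, medication, pain, and respiratory complication and intervention data are lost to the study without need.

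The size is small: 0 to 15 of 300 patients at an assumed 0 to 5%. That range is an assumption, and it takes every case to arise early enough to cut off later data. No wording recovers A1 or A2 data after the pad is removed. Even a 5% loss of those data would lower primary power by only 1.0 percentage point (95.8% to 94.8%) and one-sided key secondary power by 1.8 points (82.4% to 80.6%). This is a low-impact improvement, worth making because it is cheap.

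**What to change.** Replace the sentence in section 2.3 D with wording to this effect:

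> If irritation is significant, the PadSet is removed and RVM recording stops. Collection of all outcomes that do not need the PadSet (TOF, PACU times, medications, pain scores, respiratory complications and interventions) and the safety follow-up in section 2.5 B.8 continue unless the subject withdraws consent. Data already recorded are analysed as randomised.

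Add a cross-reference in 2.5 B.8 so that the two sections agree. Leave the existing provision for a patient who asks that data not be used.

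The change concerns data collection only. It does not address whether a patient with irritation before dosing receives the study drug, and it leaves care of the skin, including at the TOF electrode sites, to the clinicians.

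The cost is a short protocol edit with IRB review. No new assessments are needed, because the plan already collects every retained item during the PACU stay or from the medical record.
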